5.12.7. Physical and Neurological Examinations

Physical and neurological examination data will be listed.

5.12.8. Modified Clinical Institute Withdrawal Assessment – Benzodiazepines (mCIWA-B)

The clinician-observed assessment section has been removed for the modified version of CIWA-B, and the total scores of mCIWA-B ranges from 1 to 68. The total score will be summarized descriptively at the scheduled visits. Change from on-treatment Day 379 assessment will be included.

5.12.9. Columbia-Suicide Severity Rating Scale (C-SSRS)

The maximum post-baseline results from the C-SSRS will be summarized. The maximum of each subscale (suicidal ideation [Categories 1-5], suicidal behavior [Categories 6-10], suicidal ideation or behavior [Categories 1-10], and self-injurious behavior without suicidal intent) will be presented. The number of patients with suicide-related treatment-emergent events, treatment-emergent suicidal ideation, and suicidal behavior, based on a comparison of the C-SSRS at double-blind baseline and/or previous lifetime experience to maximum C-SSRS scores across all post-baseline assessments will be provided. All C-SSRS elements will be reflected in a listing.

5.12.10. Missed Visits Due to COVID-19

The number and proportion of missing visits and key assessments due to COVID-19 control measures and the frequency of remote assessments performed due to COVID-19 restrictions will be tabulated by visit, and assessment.

5.13. Pharmacokinetics

5.13.1. Pharmacokinetic Sampling

With subjects maintaining their normal BID dosing routine, a single daytime blood sample for determination of plasma CVL-865 concentration will be collected at Visits 5, 8, and 11. The date and time of the PK sample, as well as the time of ingestion of the morning dose of IMP (on the same day), will be recorded in the source documentation.

5.13.2. Pharmacokinetic Analysis

Plasma concentrations of CVL-865 in unit as reported by the analytical laboratory will be summarized by nominal time point using descriptive statistics. Summaries will include mean, standard deviation and coefficient of variation, median, minimum, maximum, and geometric mean.

Concentration values that are below the level of quantification (BLQ) will be set to zero for summary tables. The geometric mean, however, will be calculated by imputing BLQ values as $\frac{1}{2}$ BLQ. Individual values that are BLQ will be presented as “BLQ” in the concentration data listing.

Concentration data from this trial may be used to update the previously established population PK model for CVL-865. In addition, the relationship between the exposure levels (or dose) of CVL-865 and one or more efficacy/safety endpoints may be evaluated for the purpose of exploratory PK/pharmacodynamic analyses. Any population PK analysis and exploratory biomarker analyses (if completed) will be presented separately from the main clinical study report.

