### 4 TRIAL DESIGN

#### 4.1 Overall Design

This is a 57-week, active-treatment, open-label extension trial designed to assess the long-term safety and tolerability of CVL-865 as adjunctive therapy in subjects with focal onset seizures. Enrollment into the trial will consist of eligible subjects who completed the Maintenance Phase of Trial CVL-865-SZ-001.

Eligible subjects will enter this trial directly after completing Visit 4 (end of Maintenance Phase) of Trial CVL-865-SZ-001. The efficacy and safety assessments from Visit 4 of Trial CVL-865-SZ-001 will serve as the baseline assessments for the open-label trial for any assessments that are not unique to the open-label trial. All subjects must provide informed consent to participate in the open-label trial before any baseline assessments that are unique to the open-label trial are performed.

This trial is designed with a maximum duration of approximately 61 weeks during which the subjects will receive CVL-865. The trial consists of the following:

- Up to 57-week Treatment Period consisting of the following:

- 2-week double-blind Titration Phase
- 52-week Maintenance Phase
- 3-week Taper Phase
- 4-week Follow-up Period

Following enrollment in Trial CVL-865-SZ-002, subjects will enter a 2-week double-blind Titration Phase. Based on the blinded treatment group subjects were assigned to in Trial CVL-865-SZ-001, the dose will be adjusted during the double-blind Titration Phase to a final dose of 25 mg BID as shown in [Table 4](#). Subjects who completed the Maintenance Phase of Trial CVL-865-SZ-001 on a dose of 25 mg BID will remain on this dose (blinded) for the Titration Phase of Trial CVL-865-SZ-002.

Subjects who terminate during the double-blind Titration Phase (before Day 15) should receive 3 weeks of IMP to complete the Taper Phase. Please refer to [Section 7.3](#).

Subjects will continue to receive treatment with CVL-865 25 mg BID throughout a 52-week Maintenance Phase. However, this daily dose of CVL-865 can be reduced to 17.5 mg BID to address tolerability issues upon investigator discretion. Following the Maintenance Phase, subjects will be tapered off investigational medicinal product (IMP) over 3 weeks. A summary of the dosing schedule is provided in [Table 4](#).

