#### **9.4.3     *Other Analyses***

The CVL-865 concentration data will be used to determine the extent to which subjects attain exposure levels within the range predicted at each dosing regimen. Likewise, the AED concentration data will be used to review the exposure levels of AED taken with or without CVL-865. Appropriate tabular and/or graphical summaries of all PK concentration data will be generated as detailed in the SAP.

Concentration data from this trial may be used to update the previously established population PK model for CVL-865. Any population PK analysis (if completed) will be presented separately from the main CSR.

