2. OBJECTIVES AND ENDPOINTS

The trial objectives and endpoints are summarized in [Table 2](#).

Table 2. Objectives and Endpoints

Objectives	Endpoints
Primary: To assess the long-term safety and tolerability of CVL-865 as adjunctive therapy in subjects with focal onset seizures	
• Nature, frequency, and temporality of treatment-emergent adverse events (AE) (nonserious and serious), including abuse-related AEs and AEs related to medication handling irregularities• Clinically significant changes in electrocardiogram (ECG), vital sign measurements, clinical laboratory assessments, and physical and neurological examination results• Suicidality assessed using the Columbia- Suicide Severity Rating Scale (C-SSRS)• Withdrawal symptoms assessed using the Modified Clinical Institute Withdrawal Assessment – Benzodiazepines (mCIWA-B)
Exploratory: To assess the long-term efficacy of CVL-865 as adjunctive therapy in subjects with focal onset seizures	
• Focal onset seizure frequency per week over the Maintenance Phase• Seizure freedom• Seizure rate over time• Patient Global Impression of Change (PGI-C) score at each trial visit• Change from Baseline in Clinical Global Impression – Severity (CGI-S) score at each trial visit
Exploratory: To evaluate the plasma exposure of CVL-865	
• Summary listing of CVL-865 concentrations by dose and visit

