3.3. Pharmacokinetics

To evaluate the plasma exposure of CVL-865 (and anti-epileptic drug, if appropriate), a single daytime blood sample will be collected at Visits 1, 5, 8, and 11. The date and time of the pharmacokinetic (PK) sample, as well as the time of ingestion of the morning dose of IMP (on the same day), will be recorded in the source documentation.

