5. STATISTICAL ANALYSIS METHODS

5.1. General Considerations

Descriptive statistical methods will be used to summarize the data from this trial. Unless stated otherwise, the term “descriptive statistics” refers to number of subjects (N), number of observations (n), arithmetic mean, median, standard deviation (SD), first quartile (Q1), third quartile (Q3), minimum, and maximum for continuous data, and frequencies and percentages for categorical data. Certain figure presentations will include the standard error of the mean (SE). The term “treatment group” refers to treatment assignment in Trial CVL-865-SZ-001: Placebo, 7.5 mg BID CVL-865, 25 mg BID CVL-865 and assignment in Trial CVL-865-SZ-002: 25 mg BID CVL-865. All data collected from subjects who sign the informed consent form, including screen failures, will be included in data listings. Unless otherwise noted, the data listings will be sorted first by treatment, subject number and then by date within each subject number.

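### SAP 5.13.2 summarises CVL-865 concentrations by visit with no dose factor, so as written it does not match the by-dose-and-visit endpoint; the 17.5 mg BID regimen is the one misdescribed

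*SAP*

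**What the plan says.** Both documents word the exposure endpoint identically: "Summary listing of CVL-865 concentrations by dose and visit" (Protocol Section 3; SAP Section 2, Table 2). Protocol 9.4.3 gives the purpose. The data are to be used to "determine the extent to which subjects attain exposure levels within the range predicted at each dosing regimen", and the tables and graphs are left to the SAP.

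Two maintenance doses are possible. The planned dose is 25 mg BID, but Protocol 4.1 adds that "this daily dose of CVL-865 can be reduced to 17.5 mg BID to address tolerability issues upon investigator discretion", and SAP 1.4 repeats this.

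SAP 5.13.2 states that plasma concentrations "will be summarized by nominal time point using descriptive statistics". It also mentions a concentration data listing without describing its columns. Population PK and exposure-response work may be done, with any population PK reported outside the main study report. SAP 5.1 defines treatment group as "treatment assignment in Trial CVL-865-SZ-001: Placebo, 7.5 mg BID CVL-865, 25 mg BID CVL-865 and assignment in Trial CVL-865-SZ-002: 25 mg BID CVL-865".

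The SAP gives two lists of PK visits. Section 3.3 says "a single daytime blood sample will be collected at Visits 1, 5, 8, and 11". Section 5.13.1 says "a single daytime blood sample for determination of plasma CVL-865 concentration will be collected at Visits 5, 8, and 11", and adds that the date and time of the sample, "as well as the time of ingestion of the morning dose of IMP (on the same day), will be recorded in the source documentation".

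**The concern.** The endpoint has two grouping factors, dose and visit. The only summary rule in the SAP has one. The protocol's question concerns each regimen, so a figure that averages two regimens does not answer it directly. The subjects most affected are those reduced for tolerability. Their exposure would have no row of its own, and anyone taking the pooled value as theirs would read it too high.

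The mix of doses can also change from visit to visit as reductions accumulate. A pooled mean could then drift downward although exposure at each dose is constant.

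**Working it through.** Neither document gives a numerical figure on this point, so there is none to reproduce. The check is a comparison of text, followed by arithmetic to show size.

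**1. Endpoint against summary rule.** The endpoint (SAP Table 2) asks for dose and visit. The rule (SAP 5.13.2) asks for nominal time point. There is one daytime sample per PK visit (SAP 5.13.1), so nominal time point and visit are the same thing. Dose is missing.

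**2. Do the SAP's general rules supply it?** The treatment groups in SAP 5.1 are the three SZ-001 arms and 25 mg BID in SZ-002. There is no 17.5 mg BID group. Even if the PK tables were split by these groups, a 17.5 mg BID sample would stay with the 25 mg BID samples.

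**3. Could dose at sampling be derived?** Yes. The exposure CRF records daily dose (SAP 4.1.16), and SAP 5.12.1 already plans an adverse event presentation by dose at onset. The PK section does not use this.

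**4. Size of the distortion.**

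- Inputs from the documents: 25 mg BID and 17.5 mg BID, with ratio 17.5/25 = 0.70.
- Assumptions not in the documents: concentration proportional to dose, and a share f of samples at 17.5 mg BID.
- Pooled mean / 25 mg mean = (1 − f) + 0.70f = 1 − 0.30f.
- Pooled mean / 17.5 mg mean = (1 − 0.30f)/0.70.
- Pooled geometric mean / 25 mg geometric mean = 0.70^f.

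| f | Mean vs 25 mg | Mean vs 17.5 mg | Geometric mean vs 25 mg |
|---|---|---|---|
| 5% | 0.985 | 1.41 | 0.982 |
| 10% | 0.97 | 1.39 | 0.965 |
| 20% | 0.94 | 1.34 | 0.931 |
| 30% | 0.91 | 1.30 | 0.899 |
| 40% | 0.88 | 1.26 | 0.867 |

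The 25 mg mean is understated by 3% to 9% for f from 10% to 30%. Over the same range the pooled value exceeds the 17.5 mg mean by 39% to 30%.

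**5. Is Visit 1 a PK time point?** For: SAP 3.3, and the X marks at Visit 1 in the schedule grids (Protocol Table 2, SAP Table 9). Against: SAP 5.13.1, and footnote j of both schedules, which name Visits 5, 8 and 11 only. SAP Table 7 also has no baseline row, although SAP Tables 4 and 5 do. The documents do not settle it.

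**The case against.** The strongest reply is that the endpoint is itself a listing, and SAP 5.13.2 plans one. That listing could carry dose and visit, and grouping by time point does not exclude a second factor. This stands to the extent that a reader might infer that the trial cannot deliver the endpoint, or that the SAP prescribes pooling. The documents support neither reading. Pooling follows from the absence of a dose factor, and the listing is underspecified, not missing. The reply does not remove the mismatch: the listing's columns are not given, and an individual listing does not summarise exposure by regimen as Protocol 9.4.3 intends.

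A reader might also infer that SZ-001 doses are mixed into the extension results through Visit 1. They would not be. Visit 1 would be its own time point, and the SAP 5.1 groups could split it by SZ-001 arm. Only if Visit 1 were analysed, those groups were ignored and the arms were equal (an assumption) would the pooled value be (0 + 7.5 + 25)/3 = 10.8 mg, or 10.8/25 = 43% of the 25 mg level. What remains is the inconsistency over the visit list.

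A third inference is that leaving out time since dose fails the endpoint. It does not, since the endpoint asks only for dose and visit. Time since dose affects how a single daytime concentration is read against a predicted range, and the optional population PK model could use it. The documents give no half-life, so this effect cannot be sized from them.

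Finally, the distortion of the 25 mg mean is small. Even if reductions rose from 0% to 30% between visits, the spurious fall would be 9% under dose proportionality. This stands, and it limits the importance of the point.

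**Conclusion.** The point holds as a mismatch between the planned summary and the trial's own endpoint and stated purpose. SAP 5.13.2 groups by visit only, and no general rule in the SAP separates 17.5 mg BID from 25 mg BID. The 25 mg BID description would be only slightly off. The 17.5 mg BID regimen would not be described at all, and the pooled mean would misstate it by roughly a third.

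These sizes rest on two assumptions outside the documents: dose-proportional exposure, and 10% to 30% of samples at the reduced dose. The mismatch itself rests on neither. The trial has no hypothesis, its primary objective is safety, and this endpoint is exploratory and descriptive. The change is worth making because it is cheap, but no main conclusion of the trial depends on it.

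**What to change.** - In SAP 5.13.2, summarise and list CVL-865 concentrations by actual dose at sampling (25 mg BID, 17.5 mg BID) and visit, with dose taken from the exposure record.
- Specify the listing's columns, including dose at sampling, visit and time since last dose. The plan says only that dose and sample times are kept in source documents, so the sponsor should first confirm that they are in the database.
- Reconcile SAP 3.3 and the schedule grids with SAP 5.13.1, footnote j and Table 7 on whether Visit 1 is a PK time point. Show any Visit 1 results by SZ-001 arm.

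A plot against time since dose, or a percentage within the predicted range, would serve Protocol 9.4.3 further but is optional. The latter needs the predicted range to be stated, and neither document gives it.

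The cost is SAP wording and one more grouping variable, with no new procedures. The downside is small 17.5 mg BID cells; where there are few values, the individual listing will tell the reader more than the summary statistics.

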5.14. Protocol Deviations

All protocol deviations will be reviewed by the project team prior to database lock to identify subjects with important protocol deviations. Summaries of important deviations will be presented by category of deviation. All deviations from the protocol will be listed by category along with a description and any additional comments.

6. CHANGES IN THE PLANNED ANALYSES

Should any deviations from the analyses specified in the authorized statistical analysis plan arise, such deviations will be documented in the final clinical study report.

7. REVISION HISTORY

Date	Revision	Rationale

9. APPENDICES

9.1. Schedule of Assessments

Table 9. Double-blind Titration Phase and Maintenance Phase (Through Visit 12)

Trial Period/ Phases	Double-blind Titration Phase (2 weeks)		Maintenance Phase (52 weeks) Visits 2 through 12											
	Visit 1/BL ^b	Contact	Visit 2	Contact	Visit 3 ^d	Visit 4 ^d	Visit 5 ^d	Visit ^{c,d}	Visit 7 ^d	Visit 8 ^d	Visit 9 ^d	Visit 10 ^d	Visit 11 ^d	Visit 12 ^d
Visit/Contact ^a	Visit 1/BL ^b	Contact	Visit 2	Contact	Visit 3 ^d	Visit 4 ^d	Visit 5 ^d	Visit ^{c,d}	Visit 7 ^d	Visit 8 ^d	Visit 9 ^d	Visit 10 ^d	Visit 11 ^d	Visit 12 ^d
Day	1	8	15	29	43	71	99	127	155	183	211	239	267	295
Week	0	1	2	4	6	10	14	18	22	26	30	34	38	42
Window	± 3 days													
Entrance and History														
Informed consent	X													
Medical history	X													
Assign subject identification	X													
Review inclusion/exclusion criteria	X													
Review of birth control methods	X	X	X	X	X	X	X	X	X	X	X	X	X	X
Efficacy Assessments														
Review eDiary including compliance with use of eDiary	X	X	X	X	X	X	X	X	X	X	X	X	X	X
PGI-C	X		X		X		X			X			X	
CGI-S	X		X		X		X			X			X	

Trial Period/ Phases	Double-blind Titration Phase (2 weeks)		Maintenance Phase (52 weeks) Visits 2 through 12											
	Visit 1/BL ^b	Contact	Visit 2	Contact	Visit 3 ^d	Visit 4 ^d	Visit 5 ^d	Visit 6 ^d	Visit 7 ^d	Visit 8 ^d	Visit 9 ^d	Visit 10 ^d	Visit 11 ^d	Visit 12 ^d
Visit/Contact ^a	1	8	15	29	43	71	99	127	155	183	211	239	267	295
Day	0	1	2	4	6	10	14	18	22	26	30	34	38	42
Week	± 3 days													
Safety Assessments														
Physical/ neurological examination ^g	X													
ECG	X				X		X			X			X	
Vital sign measurements	X				X		X			X			X	
C-SSRS ^d	X		X		X		X			X			X	
Prior/concomitant treatments including BZD ^g	←-----→													
Adverse event monitoring ^g	←-----→													
Laboratory														
Safety laboratory blood sample	X		X		X	X	X	X	X	X	X	X	X	X
Safety laboratory urine sample	X		X		X		X			X			X	
Urine pregnancy test ^h	X		X		X	X	X	X	X	X	X	X	X	X

Trial Period/ Phases	Double-blind Titration Phase (2)		Maintenance Phase (52 weeks) Visits 2 through 12											
	Visit 1/BL ^b	Contact	Visit 2	Contact	Visit 3	Visit 4	Visit 5	Visit 6	Visit 7	Visit 8	Visit 9	Visit 10	Visit 11	Visit 12
Visit/Contact ^a														
Day	1	8	15	29	43	71	99	127	155	183	211	239	267	295
Week	0	1	2	4	6	10	14	18	22	26	30	34	38	42
Window	± 3 days													
Urine drug screening ⁱ	X													
Blood sample for PK of CVL-865 ^j	X						X			X			X	
Blood sample for PK of AEDs ^k	X						X			X			X	
Other														
IMP dispensing	X		X		X		X			X			X	
IMP compliance assessment	X	X	X	X	X	X	X	X	X	X	X	X	X	X
AED compliance assessment	X	X	X	X	X	X	X	X	X	X	X	X	X	X

Abbreviations: AED = antiepileptic drug; BL = baseline; BZD = benzodiazepine; CGI-S = Clinical Global Impression – Severity; C-SSRS = Columbia-Suicide Severity Rating Scale; ECG = electrocardiogram; ICF = informed consent form; IMP = investigational medicinal product; PGI-C = Patient Global Impression of Change; PK = pharmacokinetics.

- a. Contact with subject via phone call, internet/web, or other acceptable means of communication to check on their status.
- b. Screening/Baseline for Trial CVL-865-SZ-002 occurs at Visit 1, which is the same day as Visit 4 in Trial CVL-865-SZ-001. Any assessments conducted for Visit 4 of Trial CVL-865-SZ-001 will be considered the baseline assessments for Visit 1 of Trial CVL-865-SZ-002.
- c. Individual sites may require subjects to have COVID-19 testing done prior to enrollment. COVID-19 testing may be performed after enrollment per the investigator's discretion.
- d. In the event that a subject is unable to attend a clinic visit in person due to restrictions related to COVID-19, this visit may be completed remotely. Please refer to the Trial Operations Manual for further instructions related to remote visits.
- e. The physical examination should include weight at all time points. Physical and/or neurological examinations can be done at any time point during the trial at the investigator's discretion.
- f. The "Since Last Visit" C-SSRS form will be completed at all visits.
- g. Adverse events (serious and non-serious) and concomitant medications should be recorded from the time of signing the ICF through the subject's last visit.
- h. For women of childbearing potential only. All positive urine pregnancy test results must be confirmed by a serum test. Pregnancy tests can be performed at any time during the trial at the discretion of the investigator if pregnancy is suspected. Monthly pregnancy tests will be required for all women of childbearing potential.
- i. The urine drug screen can be conducted at any time during the trial at the discretion of the investigator.

- j. With subjects maintaining their normal BID dosing routine, a single daytime blood sample for determination of plasma CVL-865 concentration will be collected at Visits 5, 8, and 11. The date and time of the PK sample, as well as the time of ingestion of the morning dose of IMP (on the same day), will be recorded in the source documentation.
- k. One 5-mL sample for each adjunctive AED collected at Visits 5, 8, and 11.

Table 10. Maintenance Phase (Visits 13 Through 15/ET Only), Taper Phase, and Post-treatment Follow-up Phase

Trial Period/ Phases	Maintenance Phase (52 weeks) Visits 13 through 15/ET			Taper Phase (3 weeks)			Post-treatment Follow-up	
	Visit 13 ^b	Visit 14 ^b	Visit 15/ET ^c	Contact	Contact	Visit 16 ^b	Contact	Visit 17
Visit/Contact ^a	Visit 13 ^b	Visit 14 ^b	Visit 15/ET ^c	Contact	Contact	Visit 16 ^b	Contact	Visit 17
Day	323	351	379	386	393	400	407	428
Week	46	50	54	55	56	57	58	~61
Window	± 3 days							
Entrance and History								
Review of birth control methods	X	X	X	X	X	X	X	X
Efficacy Assessments								
Review eDiary including compliance with use of eDiary	X	X	X	X	X	X	X	X
PGI-C			X					
CGI-S			X					
Safety Assessments								
Physical/ neurological examination ^d			X			X		
ECG			X			X		
Vital sign measurements			X			X		
C-SSRS ^e			X			X		X
mCIWA-B			X	X	X	X	X	X
Prior/concomitant treatments including BZD use ^f	←-----→							
Adverse event monitoring ^e	←-----→							
Laboratory								
Safety laboratory blood sample	X	X	X			X		X
Safety laboratory urine sample			X			X		

Trial Period/ Phases	Maintenance Phase (52 weeks)			Taper Phase (3 weeks)			Post-treatment Follow-up	
	Visits 13 through 15/ET			Contact	Contact	Visit 16 ^b	Contact	Visit 17
Visit/Contact ^a	Visit 13 ^b	Visit 14 ^b	Visit 15/ET ^c					
Day	323	351	379	386	393	400	407	428
Week	46	50	54	55	56	57	58	~61
Window	± 3 days							
Urine pregnancy test ^f	X	X	X			X		
Other								
IMP dispensing			X					
Collect final eDiary device								X
IMP compliance assessment	X	X	X	X	X	X		
AED compliance assessment	X	X	X	X	X	X	X	X

Abbreviations: AED = antiepileptic drug; BZD = benzodiazepine; CGI-S = Clinical Global Impression – Severity; C-SSRS = Columbia-Suicide Severity Rating Scale; ECG = electrocardiogram; ET = Early Termination; IMP = investigational medicinal product; mCIWA-B = Modified Clinical Institute Withdrawal Assessment – Benzodiazepines; PGI-C = Patient Global Impression of Change.

- a. Contact with subject via phone call, internet/web, or other acceptable means of communication to check on their status.
- b. In the event that a subject is unable to attend a clinic visit in person due to restrictions related to COVID-19, this visit may be completed remotely. Please refer to the Trial Operations Manual for further instruction related to remote visits.
- c. Subjects should begin the Taper Phase after they have completed treatment in the Maintenance Phase or at the time the decision is made to discontinue. All Taper Phase and Post-treatment Follow-up procedures should be performed as indicated. If a subject discontinues early and it is inadvisable for them to taper IMP (after agreement from medical monitor), the subject should complete the Visit 17 assessments approximately 30 days following the last dose of IMP.
- d. The physical examination should include weight at all time points. Physical and/or neurological examinations can be done at any time point during the trial at the investigator's discretion.
- e. The "Since Last Visit" C-SSRS form will be completed at all visits.
- f. Adverse events (serious and non-serious) and concomitant medications should be recorded from the time of signing the ICF through the subject's last visit.
- g. For women of childbearing potential only. All positive urine pregnancy test results must be confirmed by a serum test. Pregnancy tests can be performed at any time during the trial at the discretion of the investigator if pregnancy is suspected. Monthly pregnancy tests will be required for all women of childbearing potential.

9.2. Columbia-Suicide Severity Rating Scale (C-SSRS) Suicidal Ideation and Suicidal Behavior Scores

The C-SSRS is comprised of 10 categories with binary responses. The 10 categories include:

Category 1 – Wish to be Dead

Category 2 – Non-specific Active Suicidal Thoughts

Category 3 – Active Suicidal Ideation with Any Methods (Not Plan) without Intent to Act

Category 4 – Active Suicidal Ideation with Some Intent to Act, without Specific Plan

Category 5 – Active Suicidal Ideation with Specific Plan and Intent

Category 6 – Preparatory Acts or Behavior

Category 7 – Aborted Attempt

Category 8 – Interrupted Attempt

Category 9 – Actual Attempt (non-fatal)

Category 10 – Completed Suicide

Categories 1-5 represent Suicidal Ideation and categories 6-10 represent Suicidal Behavior. Each category is scored as 1 if there is a positive response in the category and a 0 if there are no positive responses in the category.

- Self-Injurious Behavior Without Suicidal Intent During Treatment

A subject will be categorized as having self-injurious behavior without suicidal intent if there is an occurrence of non-suicidal self-injurious behavior on the C-SSRS – Since Last Visit eCRF at any post-baseline visit.

- Baseline C-SSRS Score

Baseline represents the pre-treatment assessment of recent history, with elements of suicidal ideation assessed over the prior 6 months and elements of suicidal behavior assessed over the prior 2 years. It is scaled from 0 (no suicidal ideation or behavior) to 10 (completed suicide)

- Treatment-Emergent Suicide-Related Event

A subject will be categorized as having a treatment-emergent suicide-related event if at least one post-baseline suicidal ideation or suicidal behavior score is greater than 0.

- Treatment-Emergent Suicidal Ideation Compared to Recent History

A subject will be categorized as having treatment-emergent suicidal ideation compared to recent history when there is at least one post-baseline suicidal ideation score > 0 and is an increase from baseline. Lifetime scores are not considered for baseline suicidal ideation responses.

- Treatment-Emergent Serious Suicidal Ideation Compared to Recent History

A subject will be categorized as having treatment-emergent serious suicidal ideation compared to recent history if the baseline score was < 4 and the post-baseline suicidal ideation score increases to 4 or 5. Lifetime scores are not considered for baseline suicidal ideation responses.

- Emergence of Serious Suicidal Ideation Compared to Recent History

A subject will be categorized as having emergence of serious suicidal ideation compared to recent history if baseline score was 0 (no suicidal ideation) and post-baseline C-SSRS suicidal ideation score is either 4 or 5. Lifetime scores are not considered for baseline suicidal ideation responses.

- Emergence of Suicidal Behavior Compared to all Prior History

A subject will be categorized as having emergence of suicidal behavior compared to all prior history if there had been no suicidal behavior in Categories 6-10 reported at any pre-treatment assessment, including responses to lifetime history questions, and there is at least one positive post-baseline C-SSRS assessment in Categories 6-10. 'All Prior History' represents lifetime history.

